Exposure to smoking cues will not affect how 10-repeats smoke a cigarette whereas 9-repeats will smoke more of their cigarette following cue exposure, as measured by solanesol content.

During-medication outcome variables:

Following 3 weeks of medication, measures of anxiety and depression may be reduced in baclofen-treated subjects compared to placebo-treated subjects, as evinced by lower scores on the HAM-D and HAM-A.

Throughout treatment, alcohol/other drug craving and use may be reduced in baclofen-treated subjects compared to placebo-treated subjects as measured by lower scores on the Alcohol Urge Questionnaire (AUQ) and reduced days of use as measured by the Time-Line-Follow-Back (TLFB).

Baclofen-treated subjects will show differences in how they evaluate their last cigarette smoked as measured by the modified Cigarette Evaluation Questionnaire (mCEQ).

Post-medication outcome variables

Following the 3-week imaging paradigm and 5 additional weeks of treatment, subjects treated with baclofen will have better treatment outcome, as evinced by reductions in urine cotinine levels, and cigarettes smoked per day compared to placebo-treated subjects, as measured by urine cotinine levels and cigarettes smoked per day.

Females who begin treatment in the follicular phase of the menstrual cycle and who are baclofen-treated will have better treatment outcome than females who begin treatment in the luteal phase who are baclofen-treated, as evinced by reductions in urine cotinine levels, and cigarettes smoked per day.

BACKGROUND and SIGNIFICANCE

The Problem is Relapse, motivated by Craving Cigarette smoking is the leading cause of preventable death in the nation and is the direct cause of 87% of lung cancer cases, as well as chronic obstructive pulmonary disease, emphysema and myriad other devastating and fatal diseases. Of the roughly 36 million smokers in the nation, most desire to quit, and 40% make an attempt each year, while less than 5% succeed (1, 2). The deleterious effects of smoking highlight the importance of identifying the genetic underpinnings and the brain targets that will aid in identifying effective treatments that will improve treatment outcomes.

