Clinically, baclofen has shown potential for reducing drug-motivated behaviors, including craving and relapse in opiate (59), cocaine (60-62) and amphetamine (63) addictions. However, baclofen was ineffective in a recent NIDA multi-site trial for cocaine treatment (64). The contrast of this result to earlier preclinical and human studies may reflect 1) the trial's focus on abstinence initiation rather than relapse, 2) the need for a higher baclofen dose, 3) and/or genetic makeup of the study population. Baclofen has been studied more extensively in alcohol trials and has shown promise in increasing treatment retention, decreasing WD symptoms, and reducing craving and relapse (65-69). In three case studies of alcoholics using high-dose baclofen, subjects reported complete remission, as indexed by the absence of alcohol craving and use (67, 70, 71). With respect to smokers, we observed reductions in the number of cigarettes smoked per day in a Baclofen for Smoking Reduction clinical trial using a higher dose (80mg/day) than used in previous clinical trials of drug addiction (72). To our knowledge, there are no published treatment trials of baclofen for smoking cessation.

With respect to imaging, our studies are the only published studies examining the effects of baclofen on drug cues. Using PET, and O¹⁵H₂O, we demonstrated that baclofen reduced cocaine cue-induced craving and brain activity in the amygdala and orbitofrontal and anterior cingulate cortices (73). Recently, we showed that baclofen dampened activity in the brain 'at rest' in the VS, amygdala and OFC(33).

Because of its indirect actions on the DA system, the human and animal data presented above, and the clinical and imaging data from our lab, we hypothesize that baclofen may be an effective tool to delineate a subgroup of smokers whose relapse vulnerability is more strongly influenced by SCs.

Neuroimaging and Cue Reactivity Neuroimaging techniques provide the opportunity to examine the DA-ergic system in humans and demonstrate that drug-related cues elicit DA release in the striatum in humans (74, 75). Also, as aforementioned, we observed that genetic variability in the DAT produces a profound effect on SC reactivity

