*Subjects will then participate in the 1st fMRI session and will complete a Cognitive Bias session described in detail below. At this appointment, subjects will be asked to set a Quit Date to occur one week after the second scanning session.

*Subjects will be randomized as described in detail below and participate in several study procedures over the course of the study.

*After 3 weeks, subjects will participate in the 2nd fMRI session (on treatment condition).

*Subjects will be called and reminded of their Quit Date prior to their next weekly appointment. At this appointment they will receive a "You can quit smoking booklet" and participate in a counseling session aimed at helping them recognize their relapse triggers, find alternative behaviors to engage in and get support from friends and family. They will make an attempt to quit smoking at this time.

*Subjects will continue treatment for a total treatment time of 8 weeks (i.e., 1st fMRI session followed by 3 weeks of medication treatment; 2nd fMRI session and 5 additional weeks of medication treatment).

Specific Procedures (Overview Table provided below description)

1. Initial Telephone Screening Procedures (approximately 30 min) Subjects will be recruited from the Center for the Studies of Addiction (CSA; UPenn), at [name], through local advertisement, social media (Facebook), and "word of mouth". Subjects who express interest by responding to advertising are contacted by phone and participate in a telephone screening interview. The nature of the study, including the number of visits to the center, an fMRI description, subject protections and confidentiality, are described. If the caller is still interested, questions on general health are asked. If the applicant is determined to be eligible based on this screening, s/he is asked

whether they accept or decline to participate. If the caller is still interested, they will be scheduled for an initial consenting appointment.

2. Informed Consent Procedures Visit (approximately 1 to 1.5 hr)

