Modified Cigarette Evaluation Questionnaire (mCEQ): Assesses the degree to which subjects experience the reinforcing effects of smoking. It is a standardized, validated and reliable measure with multi-item domains on smoking satisfaction, psychological reward and aversion and craving reduction. Confirmatory factor analysis exceeds 0.90. Baclofen has been shown to modify how one assesses smoking (105). This might be one mechanism underlying its potential efficacy. The mCEQ will be administered to assess the effects of baclofen on the evaluation of subject's last cigarette. (administration time: approximately 3 mins)

Blood: On scan days, all females will provide a blood sample (approx.. 2 tablespoons) for biochemical verification of cycle phase. Bloods will be tested for levels of progesterone and estradiol.

Urine Pregnancy Test: All females of childbearing potential will be assessed for pregnancy with a urine test prior to being allowed to participate in the MRI.

Urinalysis: Urines are analyzed for cotinine, the primary metabolite of nicotine, at this visit, Scan Day 2 and also at the Week 8 visit. Cotinine levels correlate with nicotine intake, which will aid in determining changes in smoking behavior. In addition, the urine sample from Scan Day 1 and 2 will be tested on-site for the presence of illicit substances. A positive result will lead to the cancellation of the scan and the exclusion of the subject from further study participation.

Cigarette filters for solanesol testing: Cigarette filters will be collected and analyzed for solanesol, a naturally occurring substance present in tobacco that provides a precise measurement of smoke exposure.

Alcohol Craving Measures – It has been shown (see Background and Significance section above) that baclofen reduces craving and relapse in alcohol dependence. Subjects in this study are not alcohol dependent, but they have varying amounts of use. Since drinking alcohol and smoking often go hand in hand, we have added the following two measures to examine whether baclofen reduces alcohol urges and/or drinking.

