The 2nd MRI session takes place after a subject has been on the medication for 3 weeks. At this session, the subject will be asked to take their medication in the presence of Study Staff [Baclofen has a short life with maximum effects at 2 hours and waning thereafter. Thus ingesting the medication in front of study staff will ensure that the medication was ingested and that its effects will be observable during the MRI as well as standardize time since dose]. Otherwise, this visit will be exactly the same as the first MRI session described above except cognitive bias testing will not be conducted.

At the weekly appointment following the second scan the subject will make a quit smoking attempt. To assist the subject in meeting this goal, study staff will meet with the subject to go through the "You can quit smoking" pamphlet during this appointment which is an interactive tool designed to help people recognize relapse triggers, provide alternative strategies when craving occurs, and how to acquire support from friends and family. Explicit instructions for how to conduct this session are included with the uploaded IRB documents (Titled: Smoking Booklet Script). Monitoring of smoking behavior is accomplished with subject Daily Diaries, weekly phone calls with study staff, weekly meetings with study staff, CO measurements and urine cotinines.

Measures collected at Weekly Study Visits

- **Adverse Events Questionnaire** is used to monitor adverse events during the administration of study medication and is administered and maintained by the study physician or nurse. Information about the onset, severity, and possible relationship to study medication, and outcome of action taken is recorded at each study visit. All locally relevant Internal Review Board (IRB) regulations and practices concerning adverse event reporting are followed. Serious adverse events will be reported to the UPenn SOM IRB within 24 hours.
- **Daily Diary:** Subjects are provided a Daily Diary in which they record medication adherence and smoking behavior (e.g., cigarettes per day, craving, pleasure received from smoking). These forms are filled out daily and collected at each visit.
- **Carbon Monoxide (CO):** A meter will be used that measure CO, which provides information on recent smoking.

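### A positive drug screen at Scan Day 2 ends all outcome collection for a randomised subject, so Week 4-8 smoking data are lost on post-randomisation behaviour; the likely bias is small and of unknown direction

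*Combined protocol and SAP*

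**What the plan says.** Under 1st MRI session Visit, the Urinalysis paragraph states that "the urine sample from Scan Day 1 and 2 will be tested on-site for the presence of illicit substances", and then: "A positive result will lead to the cancellation of the scan and the exclusion of the subject from further study participation". One sentence therefore governs two quite different time points.

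- **Scan Day 1** comes before medication starts (Study Duration), and General Procedures lists it ahead of randomisation.
- **Scan Day 2** comes on treatment: "The 2nd MRI session takes place after a subject has been on the medication for 3 weeks" (2nd MRI session Visit).

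Still to come after Scan Day 2 are the quit attempt, five more weeks of medication, the weekly diary and CO readings, and a Week 8 visit with cotinine, the Alcohol Urge Questionnaire (AUQ) and the Timeline Follow Back (TLFB). The post-medication secondary outcome rests on that period: "Following the 3-week imaging paradigm and 5 additional weeks of treatment, subjects treated with baclofen will have better treatment outcome", judged on urine cotinine and cigarettes per day. The Primary Outcome Variable(s) paragraph also includes reduction in smoking behaviour, by genotype among subjects on baclofen, and gives no time point.

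At entry, exclusion criterion 5 exempts marijuana from the urine screen, and criterion 1 admits subjects with marijuana dependence. The scan-day rule does not repeat the exemption. The Accrual item plans 100 randomised with 15 expected losses. The Analyses section names no analysis set and no method for missing data. Stopping Procedures provides for monitoring while a subject is weaned off drug, which is safety follow-up and not outcome follow-up.

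**The concern.** At Scan Day 1 the rule works as an eligibility screen and does no harm to the arm comparison. At Scan Day 2 the same words remove randomised subjects because of something they did on treatment. A comparison limited to observed Week 4-8 data would then contrast two groups filtered after randomisation, and randomisation would no longer guarantee that they are alike.

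Baclofen need not change drug use for this to matter. Equal exclusion rates can still bias the comparison if the excluded differ from the retained by different amounts in the two arms. What is at stake is the arm comparison of cotinine and cigarettes per day at the end of treatment, the Week 8 AUQ and TLFB data, and any Week 4-8 reading of the smoking-behaviour part of the primary outcome. Aim 1, which rests on the pre-medication scan, is untouched. The second-scan images of a positive subject would be missing under any sensible rule, so the imaging part of Aims 2 and 3 is not the issue.

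**Working it through.** **The plan's own figure.** The only sample-size statement concerns genotype groups: 18-24 per group for effect sizes 0.98 and 0.78. With n = 2(1.960 + 0.842)²/d² (two-sided 0.05, 80% power), d = 0.98 gives 17 and d = 0.78 gives 26, close to the stated range. It says nothing about the baclofen-placebo comparison at Week 8, so it does not bear on this point.

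**Inputs from the documents.** 100 randomised, 2:1 allocation, 15 expected losses.

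**Inputs assumed.** The documents give no positive-screen rates and no outcomes for excluded subjects. Let p be the share of an arm excluded at Scan Day 2, and D how much more the excluded smoke than the retained in that arm, in SD units (P placebo, B baclofen). I take p = 5% or 10% and D = 0.5 or 1.0 in each arm.

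**Standard error (SE) of the arm difference.**
- All randomised, 67 v 33: sqrt(1/67 + 1/33) = 0.213 SD.
- After 15 losses, 56.7 v 28.3: sqrt(1/56.7 + 1/28.3) = 0.230 SD.
- Smallest difference detectable with 80% power at 85 subjects: 2.80 × 0.230 = about 0.64 SD.

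**Bias.** Each arm's full mean is its retained mean plus p × D. The retained-only difference (baclofen minus placebo, higher meaning more smoking) therefore departs from the all-randomised difference by

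bias = pP × DP − pB × DB.

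A positive value understates a baclofen benefit, and a negative value overstates it.

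The product p × D takes the values 0.025, 0.05, 0.05 and 0.10. The 16 placebo-minus-baclofen combinations are:

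| Bias (SD) | −0.075 | −0.05 | −0.025 | 0 | +0.025 | +0.05 | +0.075 |
|---|---|---|---|---|---|---|---|
| Combinations | 1 | 2 | 2 | 6 | 2 | 2 | 1 |

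Fourteen of the 16 lie within 0.05 SD. Against the SE of 0.230, 0.05 SD is 0.22 SE and 0.075 SD is 0.33 SE. Equal rates do not guarantee zero: 10% in both arms with DP = 0.5 and DB = 1.0 gives 0.05 − 0.10 = −0.05 SD, which favours baclofen.

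**If losses are larger,** for example because marijuana counts:
- 15% placebo, 5% baclofen, D = 1.0 in both: 0.15 − 0.05 = +0.10 SD (0.10/0.64 = 16% of the detectable difference).
- 30% and 15%, D = 1.0 in both: 0.30 − 0.15 = +0.15 SD (23%). This is a stress case. It implies about 10 exclusions in each arm, more than the 15 losses planned in total.

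**Precision.** If these exclusions are among the 15 planned losses, there is no added cost. If they are extra, the SE rises by 1/sqrt(0.95) = 1.026 (2.6%) or 1/sqrt(0.90) = 1.054 (5.4%).

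**How many subjects an amendment could still reach.**
- From 12/01/2012 to this version (1/6/2017) is 1,497 days, or 4.10 years. At 20-25 a year, 82 to 102 would already be randomised.
- From this version to 08/31/2017 is 237 days, room for 237/365 × 20 to 25 = 13 to 16 subjects before the cap of 100 is applied.
- With the cap, 20 a year leaves 13, about 21 a year leaves the maximum of about 14, and 25 a year leaves none.
- At 5-10% positive, that is 0 to 1.4 subjects, plus any already randomised but not yet at Scan Day 2.

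**The case against.** **Safety and image quality justify removal.** Recent drug use would confound the scan, and the Protection text for baclofen warns against combining it with sedating drugs. That supports cancelling the scan and, where the physician sees fit, stopping study drug. It gives no reason to stop collecting diaries, CO and cotinine at visits already scheduled.

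**Positives will be few.** Probably so: subjects have been screened at consent, at the physical and at Scan Day 1. But the first two screens let marijuana through. If the scan-day rule counts it, Scan Day 1 is the only earlier screen for it, though that should remove many regular users before medication starts.

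**The bias presupposes an analysis the plan does not specify.** This stands. The plan states no retained-only comparison. Counting losses as continuing smokers, or modelling the Week 1-3 diaries, is not ruled out. The concern is therefore conditional: it applies to any analysis limited to observed Week 4-8 data, and nothing in the plan excludes one.

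**It is part of a wider missing-data gap.** Also largely true. One statement covering all 15 expected losses could carry the analysis side. It could not recover outcomes that the rule itself prevents from being collected.

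**The range is symmetric by construction.** Correct. Both arms were given the same assumed inputs, so the symmetry reflects ignorance about direction and is not evidence that the bias is centred on zero.

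**Conclusion.** The point stands as a minor one. The rule is explicit, it acts after randomisation, and nothing in the documents keeps a Scan Day 2 positive in outcome follow-up. Under assumed exclusion rates of 5-10% and outcomes 0.5-1.0 SD worse in the excluded, the bias in an observed-data comparison is at most 0.075 SD, or 0.33 SE, in either direction. "Small" rests on those assumptions and on positives being few; the marijuana ambiguity is the main reason they might not be.

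Three stronger readings are tempting and not supported.

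- **That baclofen will lower drug use, so exclusions will fall mainly on placebo and hide a benefit.** The plan says only that "alcohol/other drug craving and use may be reduced in baclofen-treated subjects compared to placebo-treated subjects", and its two named measures are described as alcohol measures: "we have added the following two measures to examine whether baclofen reduces alcohol urges and/or drinking". The Background cites potential for "reducing drug-motivated behaviors, including craving and relapse in opiate (59), cocaine (60-62) and amphetamine (63) addictions", but then reports a multi-site cocaine trial in which baclofen was ineffective. The direction is unknown.
- **That only secondary outcomes are affected, or that the primary outcome is compromised.** Cotinine and cigarettes per day are listed as secondary, yet smoking behaviour also appears, undated, in the primary outcome text. Neither claim can be settled from the documents.
- **That amending the rule would rescue many subjects.** With the cap of 100, it would prospectively retain about 0-1 subject, plus any already randomised and awaiting Scan Day 2.

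**What to change.** **Rule.** Keep exclusion for a positive screen at Scan Day 1. At Scan Day 2, a positive cancels that scan only, and the imaging is recorded as missing. The study physician decides whether study drug continues, with the taper if it is stopped. The subject stays in the scheduled outcome visits (diary, CO, Week 8 cotinine, AUQ, TLFB) and is analysed in the assigned arm. State whether marijuana counts as a positive on scan days.

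**Subjects already excluded.** Report Scan Day 2 exclusions by arm. Add a sensitivity analysis that includes these subjects as randomised, for instance with smoking set at baseline level; that value is one choice among several and should be labelled so. A single missing-data statement for all expected losses can carry this.

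**Cost.** A one-paragraph amendment with no new visits. The downside is a few subjects with outcome data, possibly off drug, and no second scan. Because few subjects remain to be reached, most of the benefit comes from the counts by arm and the sensitivity analysis, which let a reader judge whether the Week 8 comparison was affected.
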